6.3.1.3. Sensitivity Analyses with COVID-19 Cases Counted Starting at Various Timepoints

Sensitivity analyses will be performed with COVID-19 cases counted starting at various timepoints as below using the PP Set. The censoring rules for analyses of the primary endpoint are summarized in Table 2.

- immediately after the second injection of IP
- 14 days after the first injection of IP (also as primary analysis approach for the secondary efficacy objective: To evaluate the efficacy of mRNA-1273 to prevent COVID-19 after the first dose of IP.)
- immediately after the first injection of IP
- immediately after randomization

If <10% of the COVID-19 cases received the first injection after the day the subject was randomized, sensitivity analysis with COVID-19 cases counted starting after the first injection of IP may not be performed separately, as it would be very similar to the sensitivity analysis with COVID-19 cases counted starting from randomization.

Table 2: Censoring Rules for COVID-19

Situation	Primary Efficacy Approach (cases ≥ 14 days after Dose 2)	Sensitivity Analyses			
		Cases starting after Dose 2	Cases ≥ 14 days after Dose 1	Cases starting after Dose 1*	Cases starting after randomization
Early case from randomization up to first injection	Censored at date of case	Censored at date of case	Censored at date of case	Censored at date of case	Event
Early case from Dose 1 up to ($<$) 14 days after Dose 1	Censored at date of case	Censored at date of case	Censored at date of case	Event	Event
Early case from ≥ 14 days after Dose 1 up to ($<$) Dose 2	Censored at date of case	Censored at date of case	Event	Event	Event
Early case from Dose 2 up to ($<$) 14 days after Dose 2	Censored at date of case	Event	Event	Event	Event
Case ≥ 14 days after Dose 2	Event	Event	Event	Event	Event
Early discontinuation or death without documentation of COVID-19	Censored at date of discontinuation/death				

Situation	Primary Efficacy Approach (cases \geq14 days after Dose 2)	Sensitivity Analyses			
		Cases starting after Dose 2	Cases \geq14 days after Dose 1	Cases starting after Dose 1*	Cases starting after randomization
Early infection as detected by: positive RT-PCR at scheduled visit (pre-dose 2), or, positive bAb against SARS-CoV-2 NP in blood samples at the scheduled visits	Censored at date of early infection				

* To be performed if there are \geq 10% of total cases with Dose 1 date > randomization date

Analysis of the primary efficacy endpoint based on the mITT Set will also be performed using the same statistical methods used for the primary analysis. The above sensitivity analyses will be also performed with COVID-19 cases counted starting at various timepoints using the mITT Set.

6.3.1.4. Subgroup Analysis

To assess consistency of VE across various subgroups, subgroup analyses of the primary efficacy endpoint will be performed in select subgroups specified below based on the PP Set. The primary efficacy endpoint will be analysed by each of the subgroups using the same methods described for the primary analysis, i.e. the stratified Cox proportional hazard model with Efron's method of tie handling with a single treatment covariate, and the estimate of VE and its 95% CI will be provided within each category of the following classification variables:

- Age groups: ≥ 18 and < 65 years, ≥ 65 years
- Age groups: ≥ 18 and < 65 years, ≥ 65 years and < 75 years, and, ≥ 75 years
- Stratification factor at randomization: ≥ 18 and < 65 years and not at risk, ≥ 18 and < 65 years at risk, ≥ 65 years
- Sex (female, male)
- Race
- Ethnicity
- Race and Ethnicity: non-Hispanic white, communities of color
- Each risk factor for severe COVID-19 illness as listed in Section 6.2.1 of the protocol

If the number of subjects in certain subgroups are too small, it may be combined with the other subgroups for the subgroup analyses. Forest plots will be provided for VE and its 95% CI for the subgroup analyses based on PP Set. Subgroup analyses based on the mITT Set may be performed.

Recently, new SARS-CoV-2 variants have emerged. COVID-19 cases may be sequenced and depending on the findings, summary of cases genotypically distinct and genotypically similar to vaccine by treatment assignment may be provided. Analysis of vaccine efficacy against variants may be performed if there are sufficient numbers of variants cases.

6.3.1.5. Supportive Analysis Using Exact Method Based on Incidence Rate

Incidence rate will be provided for each treatment group. Incidence rate will be calculated as the number of subjects with an event (i.e. first occurrence of COVID-19 at least 14 days after the second injection) divided by the number of subjects at risk adjusted by person-time (years) in each treatment group. The person-time is calculated as the time from randomization to the date of the first event for subjects with an event, and the time from randomization to the date of censoring for subjects without an event (or who are censored). Person-time, incidence rate, and 95% CI for incidence rate will be provided by treatment group.

As a supportive analysis, VE will also be estimated by one minus the ratio of incidence rate (mRNA-1273 vs. placebo), i.e. $1 - \text{ratio of incidence rate (mRNA-1273 vs. placebo)}$ adjusting for person-time, and the 95% CI of VE will be computed using the exact method conditional upon the total number of cases adjusting for person-time.

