There is a theoretical risk that active vaccination to prevent the novel viral infection caused by SARS-CoV-2 may cause a paradoxical increase in the risk of disease. This possibility is based on the rare phenomenon of vaccine-associated disease enhancement which was first seen in the 1960s with 2 vaccines made in the same way (formalin-inactivated whole virus) and designed to protect children against infection with respiratory syncytial virus ([Chin et al 1969](#)) or measles ([Fulginiti et al 1967](#)). Disease enhancement has also been proposed as a possible explanation for cases of more serious disease associated with dengue vaccination ([Thomas and Yoon 2019](#); [WHO 2019](#)).

To monitor the risk of enhanced disease in this study, an independent Data and Safety Monitoring Board (DSMB) will review unblinded cases of COVID-19 to assess for inefficacy and also for numerical imbalance in cases of both COVID-19 and severe COVID-19 with the purpose of providing a non-binding recommendation to the Sponsor ([Section 8.4.2](#)). To date, clinical immunogenicity data from the DMID Phase 1 study of mRNA-1273 demonstrated high levels of nAbs and Th-1-polarized CD4+ T-cell responses ([Jackson et al 2020](#)). In addition, in Study P301, after a median follow-up of 2 months after the second dose of vaccine, the overwhelming majority of COVID-19 cases occurred in participants who received placebo rather than mRNA-1273 ([Baden et al 2020](#)), consistent with a low risk of enhanced respiratory disease following vaccination with mRNA-1273. These data suggest that a paradoxical increase in the risk of disease, while not eliminated, is likely to be low. Further details are provided in the current IB.

In the context of the EUA for individuals 18 years and older for mRNA-1273, there have been very rare reports of myocarditis and pericarditis occurring after vaccination with Moderna

COVID-19 vaccine. Further details about this risk are described in the Fact Sheets (available on www.fda.gov). Although causality has not been established, the majority of the cases have been reported in young males shortly after the second dose of the vaccine. These are typically mild cases and individuals tend to recover within a short time following standard treatment and rest ([Gargano et al 2021](#)).

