For the primary analysis, subjects who have no documented COVID-19 will be censored at the last study assessment date. Subjects who discontinue the study early or die due to causes unrelated to COVID-19 without documented COVID-19 will be censored at the date of early discontinuation or death. Subjects who experience an early COVID-19 up to 14 days after the second injection of IP will be censored at the time of documented COVID-19.

As in PP Set definition, subjects who missed study IP administration, who were seropositive at baseline, or who had major protocol deviations that impact critical or key data, will be excluded from the PP Set.

The number and percentage of subjects who had an event (i.e. the first occurrence of COVID-19 at least 14 days after the second injection) will be reported.

Potential intercurrent events to the estimand are listed in Appendix F Table 9. The primary estimand with rationale for strategies to address intercurrent events is summarized in Appendix F 10.

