6.4.2.1. The First Interim Analysis

The primary efficacy endpoint of mRNA-1273-P301 is COVID-19, defined as the first occurrence of COVID-19 starting 14 days after the 2nd injection.

For the primary efficacy objective, the null hypothesis of this study was that the vaccine efficacy (VE) of mRNA-1273 to prevent first occurrence of COVID-19 is ≤ 30%, i.e.

H₀^{efficacy}: VE ≤ 0.3.

The first interim analysis was conducted based on a data snapshot occurred on 11-Nov-2020 whereas the data cut-off date for efficacy was 07-Nov-2020. At IA1, the median follow-up time was 49 days (7 weeks). The primary analysis of COVID-19 is based on the Per-Protocol (PP) set with cases starting 14 days after the 2nd dose. The IA1 efficacy analysis was performed by the independent biostatistician and the results were first reviewed by the independent external DSMB on 15-Nov-2020. The DSMB concluded that

“with 63% of the expected number of the total number of adjudicated primary endpoints, the study has passed the efficacy monitoring boundary for benefit.” The DSMB “encourages the study team to prepare the data for the FDA package as rapidly as possible.” Based on the DSMB’s recommendation, select Sponsor and CRO personnel were unblinded to prepare for regulatory submissions.

Vaccine efficacy of mRNA-1273 was demonstrated at IA1 based on the pre-specified success criterion on efficacy. As efficacy was demonstrated at IA1 based on 95 cases per adjudication committee, all subsequent efficacy analyses, if any, would be considered supportive or supplementary.

At IA1, the total number of COVID-19 starting 14 days after the 2nd injection based on the adjudication committee assessments (i.e. primary efficacy endpoint) was 95, 63% of the information fraction based on the total target number of 151. Correspondingly, the nominal one-sided alpha is 0.0047. At IA1, the one-sided p-value to test null hypothesis of VE \leq 30% from the stratified Cox proportional hazard model was <0.0001 , and was compared to the nominal one-sided alpha (0.0047) based on the number of cases at IA1 (95 in total). Equivalently, the lower-bound of the alpha-adjusted confidence interval of VE, the two-sided 99.1% CI, can be compared to 30% at IA1. The lower bound of the two-sided 99.1% CI was above 30% at IA1.

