6.4.2.2. The Primary Analysis of Efficacy

To support regulatory submissions, in particular, to provide data with a median follow-up duration for safety and efficacy of at least two months after completion of the full vaccination regimen, a decision was made to perform a second analysis based on the data snapshot as of 25-Nov-2020 (DS2, whereas the data cut-off date for efficacy was 21-Nov-2020). Both safety and efficacy analyses were performed to provide additional information on the vaccine’s profile. As efficacy has been demonstrated at IA1, the analysis of efficacy based on the data snapshot of 25-Nov-2020 were supplementary in nature.

The date cutoff date for efficacy in the second analysis of efficacy was 21-Nov-2020. All potential COVID-19 cases starting 14 days after the 2nd injection confirmed by RT-PCR

(central or local), with corresponding minimal clinical data in electronic data capture (EDC) as of 21-Nov-2020 were sent to the Adjudication Committee. All these potential cases have been adjudicated for this analysis.

It was anticipated that the total number of COVID-19 cases based on the adjudication committee assessments starting 14 days after the 2nd injection in the Per-Protocol Set at DS2 on 25-Nov-2020 would be ≥ 151 , the target total number of events at the originally planned primary analysis. Therefore, this analysis was considered the primary analysis of efficacy of at least 151 cases, as prespecified in the protocol. At DS2, the total number of COVID-19 cases based on the adjudication committee assessments starting 14 days after the 2nd injection in the Per-Protocol Set was 196.

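### Part A incidence rates count cases from 14 days after Dose 2 but person-time from randomization, so the absolute rates are low, relative to time at risk, by roughly a fifth to a third

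*SAP*

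**What the plan says.** Part A SAP 6.3.1.5 takes as its event the "first occurrence of COVID-19 at least 14 days after the second injection". The rate is the number of participants with that event "divided by the number of subjects at risk adjusted by person-time (years) in each treatment group". It then fixes the start of the clock: "The person-time is calculated as the time from randomization to the date of the first event for subjects with an event". Participants without an event contribute from randomization to censoring. Person-time, the rate and its 95% CI are reported by arm, and a supportive vaccine efficacy (VE) is formed as one minus the rate ratio.

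Section 6.3.1.2 settles what happens to earlier cases: "Subjects who experience an early COVID-19 up to 14 days after the second injection of IP will be censored" at the time of that case. Table 2 (6.3.1.3) says the same. The nominal dose interval is 28 days, and the Per-Protocol (PP) Set admits 21 to 42 days (5.4).

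Two other places treat the start of risk differently from 6.3.1.5. The assumptions in protocol 9.3 put participants at risk only from 14 days after Dose 2. The Part B/C SAP (5.3.1.2.1) starts person-time at the beginning of each counting interval, one of which is the period from 14 days after Dose 2.

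**The concern.** A participant cannot contribute a countable case before 14 days after Dose 2, but those days are in the denominator. The section describes its denominator in terms of participants at risk, so a reader will take the result as a rate over time at risk, and it is not one. Both confidence limits move by the same factor as the rate, so the interval gives no warning.

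What is at stake is the absolute level of the rates. The Part B/C SAP recomputes matched rates for the mRNA-1273 primary series, but not the blinded placebo rate. Anyone who wants that rate as a benchmark must take it from Part A, on a different denominator.

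**Working it through.** **1. Which start of risk do the plan's own figures use?** Inputs from protocol 9.3: 30,000 randomized, 15% excluded from the PP Set (25,500 remain), 6-month incidence 0.75% on placebo and 0.30% on vaccine, 2% annual dropout, 3-month uniform accrual. With exponential hazards, the times to 53, 106 and 151 cases are:

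- risk from day 42: 5.3, 7.7 and 9.7 months, which round to the stated 5, 8 and 10;
- risk from randomization: 3.9, 6.3 and 8.3 months, which do not match.

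The protocol's planning figures therefore carry the 42-day lead-in.

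**2. Formula.** The lead-in is 28 + 14 = 42 days nominally (21 + 14 = 35 to 42 + 14 = 56 for individuals under the PP window). With N participants and mean follow-up F days from randomization, person-time at risk is about N(F − 42) and person-time as specified is NF. The specified rate is (F − 42)/F of the at-risk rate, so it is low by 42/F. Exact Poisson limits for the count are divided by the same person-time and shrink by the same factor.

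**3. Bracketing F.** F is not stated. The anchor is the 49-day median at the 07 Nov 2020 efficacy cutoff (Part A SAP 6.4.2.1), whose origin is not given. The end of blinded follow-up is bracketed by 23 Dec 2020 (Amendment 6, which introduced the decision visit) and 26 Mar 2021 (data cutoff, Part B/C SAP Introduction).

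| 49 days counted from | Median Dose 2 (2020) | Days after Dose 2 at 21 Nov 2020 | Median randomization (2020) | F | 42/F |
|---|---|---|---|---|---|
| Dose 2 | 19 Sep | 63 | 22 Aug | 123 to 216 | 34.1% to 19.4% |
| 14 days after Dose 2 | 5 Sep | 77 | 8 Aug | 137 to 230 | 30.7% to 18.3% |
| Randomization | 17 Oct | 35 | 19 Sep | 95 to 188 | 44.2% to 22.3% |

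The third column tests the origin. The analysis with the 21 Nov 2020 cutoff was meant to supply a "median follow-up duration for safety and efficacy of at least two months after completion of the full vaccination regimen" (6.4.2.2), and protocol 2.3.2 reports results "in Study P301, after a median follow-up of 2 months after the second dose of vaccine". The last row, at 35 days, does not fit; the first fits best. At the midpoint of its range, (123 + 216)/2 = 169.5 days, the shortfall is 42/169.5 = 24.8%. A simulated placebo arm with Dose 2 timing varied inside the PP window gave 34.2% and 19.5% at the two ends.

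**4. Illustration at planning rates (not the trial's data).** Take 15,000 × 0.85 = 12,750 PP placebo participants, hazard −ln(1 − 0.0075)/182.5 per day, F = 169.5, and no dropout or early cases. That gives 67 cases over 4,439 person-years at risk, or 5,905 from randomization:

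- at risk: 15.1 per 1,000 person-years (95% CI 11.7 to 19.2);
- as specified: 11.3 (8.8 to 14.4).

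**5. VE from the rate ratio.** With mean follow-up Tv on vaccine and Tp on placebo, the specified ratio is the at-risk ratio times [(Tv − 42)/Tv] / [(Tp − 42)/Tp]. This factor is 1 when Tv = Tp. As a purely assumed imbalance, placebo follow-up 5 to 20 days shorter around a mean of 150 days gives factors of 1.013 (152.5 and 147.5 days) to 1.054 (160 and 140 days). A VE of 94.5% becomes 94.43% to 94.21%; a VE of 60% becomes 59.48% to 57.86%.

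**The case against.** **The convention is disclosed and consistent.** The SAP states its denominator openly, measures time to COVID-19 from randomization (6.3.1.1) and starts the blinded efficacy period there (6.1, 6.4.3). The output is a valid rate per person-year from randomization. This stands to the extent that the rate is low only relative to time at risk. It does not dispose of the point, because 6.3.1.5 itself speaks of participants at risk and protocol 9.3 starts risk 14 days after Dose 2.

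**The consequence is small.** The analysis is supportive. No document plans to set Part A rates beside Part B/C rates, and protocol 9.5.1.3 keeps long-term efficacy descriptive, without comparing cohorts. Nor is the Part B/C SAP uniformly interval-matched: its variant-specific analysis (5.3.1.4) runs person-time from Dose 1 or from the booster. All of this stands and limits the weight of the point.

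**The range is inferred.** It needs an origin for the 49 days, medians used as means, and a nominal 42-day lead-in. This also stands; the mechanism is firmer than the percentages.

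Two stronger readings are tempting.

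- A reader might apply the arithmetic to the November 2020 cutoffs (42/77 = 55% and 42/91 = 46%). The documents do not support that. Those analyses preceded version 2.0 of the SAP (08 Mar 2021); version 1.0 was the plan finalized before the first interim analysis, and its person-time rule is not in the documents.
- A reader might infer that the efficacy finding is biased. It is not affected: the Cox model, the tests and the boundaries do not use these rates.

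**Conclusion.** The point holds for the Part A rates at the final blinded analysis under the primary counting rule. Each arm's incidence rate and both 95% limits are low, relative to time at risk, by about 42/F. On the best-supported reading of the dates this is about 34% to 19%, or about 31% to 18% if the 49 days run from 14 days after Dose 2.

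The size rests on four assumptions: the origin of the 49 days, medians standing in for means, a 42-day lead-in (35 to 56 under the PP window), and fewer than half of participants having left blinded follow-up before 23 Dec 2020. The direction rests on none of them.

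The effect is confined to descriptive absolute rates. VE from the rate ratio is essentially unchanged when follow-up is balanced by arm; the documents give no figure for any imbalance.

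**What to change.** For the primary counting rule, start person-time 14 days after Dose 2, among participants still event-free and uncensored on that date. Those who never reach it contribute neither cases nor person-time. Other Part A rates with a different counting date (6.3.1.3, 6.3.2.2) should take the matching start; where cases count from randomization, the present rule already fits.

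The Part B/C SAP Introduction treats the Part A analyses as complete and reported. The at-risk rates should therefore be given as a supplement, and the existing ones labelled as per person-year from randomization. The existing rates should not be set beside the Part B/C rates for the interval from 14 days after Dose 2. The Cox analysis needs no change.

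The cost is one sentence in the SAP and a changed start date in the derivation, with no new data. The downside is two sets of absolute rates to reconcile.

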6.3.2. Analysis of the Secondary Efficacy Endpoints

A sequential/hierarchical testing procedure will be used to control type 1 error rate over the primary efficacy endpoint and the secondary efficacy endpoints. Secondary efficacy endpoints will only be tested when the primary efficacy endpoint achieves statistical significance. Multiplicity adjustments among the secondary efficacy endpoints may be performed for secondary efficacy endpoints as described in Section 6.5.

6.3.2.1. Derivation of Secondary Efficacy Endpoint: Severe COVID-19

Derivation of select secondary efficacy endpoints are included in this section.

6.3.2.1.1. Derivation of Secondary Efficacy Endpoint: Severe COVID-19

Severe COVID-19 is defined as:

To be considered severe COVID-19, the following criteria must be met:

- Confirmed COVID-19 as per the Primary Efficacy Endpoint case definition, AND
- any of the conditions listed in Section 3.2.1 (Section 8.1.1 of the protocol).

The date of documented severe COVID-19 will be the later date of:

- Date of documented COVID-19,
- Date of eligible symptom for severe COVID-19, defined as the earliest of the first eligible severe symptom is reported

The date of eligible symptoms for severe COVID-19 should be within 28 days after the positive RT-PCR result used in the confirmation of COVID-19.

The time to the first occurrence of severe COVID-19 will be calculated as:

Time to the 1st occurrence of severe COVID-19 = Date of documented severe COVID-19 – Date of randomization +1

The independent AC blinded to treatment assignments will adjudicate severe COVID-19 events. Two sets of severe COVID-19 will be provided:

- Based on Adjudication Committee assessments
- Based on eligible symptoms for severe COVID-19, and positive RT-PCR.

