If scheduled, a study site Illness Visit includes assessments such as medical history, physical examination, blood sampling for clinical laboratory testing, and 2 NP swabs, 1 for viral polymerase chain reaction (PCR) SARS-CoV-2 testing and 1 for multiplex PCR testing for respiratory viruses, to evaluate the severity of the clinical case. Radiologic imaging studies may be conducted. Blood samples will be collected for potential future immunologic assessment of SARS-CoV-2 infection. Every effort to complete an Illness Visit that includes both the NP swabs and blood draw should be made by the site, even in the presence of a local positive or negative Clinical Laboratory Improvement Amendments (CLIA) certified or CLIA-certified waiver laboratory result for the participant.

Cases are defined as participants meeting clinical criteria based both on symptoms for COVID-19 and on RT-PCR detection of SARS-CoV-2 from samples collected within 72 hours of the study participant reporting symptoms meeting the definition of COVID-19. Participants who are hospitalized for COVID-19 without the opportunity for a clinic or home visit will also be considered cases, assuming that the symptomatology criteria for COVID-19 are met and a respiratory sample is positive for SARS-CoV-2 by PCR at a CLIA-certified or CLIA-certified waiver laboratory. Investigators are encouraged to try to obtain a respiratory sample during the course of hospitalization for submission to the study central laboratory, if feasible. The investigator should determine if the criteria for severe COVID-19 has been met.

Evidence of severe COVID-19 is defined as in [Section 8.1.1](#).

All clinical findings will be recorded in the eCRF. All confirmed cases of COVID-19 will be captured as MAAEs, along with relevant concomitant medications and details about severity, seriousness, and outcome.

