6.3.1. Analysis of the Primary Efficacy Endpoint

6.3.1.1. Primary Efficacy Endpoint Definition/Derivation

The primary efficacy objective is the VE of mRNA-1273 to prevent occurrence of COVID-19 starting 14 days after the second dose of IP. COVID-19 is defined as symptomatic disease based on the criteria specified in [Section 8.1.1](#) of the protocol. Cases

are defined as participants meeting clinical criteria based both on symptoms for COVID-19 and positive RT-PCR test results.

Subjects reporting COVID-19 symptoms, as defined in Section 8.1.2 of the protocol, will be asked to use an eDiary to report COVID-19 symptoms, and an Illness Visit will be scheduled to collect an NP swab if COVID-19 symptoms are reported (refer to Section 8.1.2 of the protocol).

For the primary efficacy endpoint, a COVID-19 case will be identified as a positive post-baseline RT-PCR test result that is prompted by symptom(s), together with eligible symptoms, i.e. a positive PCR result of the eligible symptoms summarized below in Table 1.

An independent Adjudication Committee (AC) blinded to treatment assignments will review potential cases and adjudicate COVID-19 and severe COVID-19 events and the date of COVID-19 and severe COVID-19.

Two sets of COVID-19 will be provided:

- Based on Adjudication Committee assessments
- Based on eligible COVID-19 symptoms (at least 2 systemic symptoms or 1 respiratory symptom) and positive RT-PCR.

Table 1: Derivation for COVID-19 (primary efficacy endpoint)

	COVID-19
Post-baseline PCR results at illness visits prompted by symptom(s)	Positive, AND
Systemic Symptoms	at least TWO of the following systemic symptoms : Fever ($\geq 38^{\circ}\text{C}$), chills, myalgia, headache, sore throat, new olfactory and taste disorder(s); OR

Respiratory symptoms	at least ONE of the following respiratory signs/symptoms: cough, shortness of breath or difficulty breathing, OR clinical or radiographical evidence of pneumonia;
----------------------	--

The date of documented COVID-19 (case) will be the later date of ([2 eligible systemic symptoms reported, or 1 eligible respiratory symptom reported] and, [date of positive PCR test]). Specifically, the date of documented COVID-19 will be the later date of the following two dates (date of positive PCR test, and the date of eligible symptom(s)), and the two dates should be within 14 days of each other.

- Date of positive PCR test,
- Date of eligible symptom(s), defined as earliest of

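### In the programmed severe COVID-19 set, the 28-day window has no look-back, so a case whose first severe sign was reported before the positive sample is not classed as severe

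*SAP*

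**What the plan says.** The Part A SAP, 6.3.2.1.1, builds severe COVID-19 from a case confirmed under the primary definition plus any one of the listed severity criteria. It makes three timing statements:

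- The severe-sign date is "defined as the earliest of the first eligible severe symptom is reported".
- "The date of documented severe COVID-19 will be the later date of" two dates, the documented COVID-19 date and the severe-sign date.
- "The date of eligible symptoms for severe COVID-19 should be within 28 days after the positive RT-PCR result used in the confirmation of COVID-19".

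Two sets of severe cases are then produced. One is "Based on Adjudication Committee assessments". The other is "Based on eligible symptoms for severe COVID-19, and positive RT-PCR", called the programmed set here.

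The neighbouring rules differ. For the primary endpoint (SAP Part A, 6.3.1.1) the test date and the symptom date are linked by the condition that "the two dates should be within 14 days of each other". The secondary COVID-19 definition (6.3.2.1.2) uses the same condition. Protocol 8.1.1 defines severe COVID-19 as a confirmed case plus any severity criterion and says nothing about which came first. Protocol 8.1.2 adds that "Participants who are hospitalized for COVID-19 without the opportunity for a clinic or home visit will also be considered cases", provided that the symptom criteria are met and a respiratory sample is positive.

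The Part B/C SAP (5.3.2.1.1) takes the severe definition from the Part A SAP and restates only the time origin.

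**The concern.** The first reported sign supplies the date, and that date must follow the positive test. Put together, the two statements leave out any confirmed case whose first severe sign was reported before the sample. Persistence or worsening after the sample cannot bring the case back, because a later sign never becomes the severe-sign date.

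The sequence is foreseeable. Swabs are prompted by symptoms and may be taken up to 72 hours later, or as soon as possible. A participant admitted without an Illness Visit may have respiratory failure or low oxygen saturation charted before the positive respiratory sample. Such a participant can be a valid COVID-19 case under the two-sided rule, meet the protocol's severity criteria, and still be programmed as non-severe.

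At stake is the value of the programmed set as a check on adjudication. If the two sets disagree because of a window, the disagreement says nothing about case quality. The rule also carries into Parts B and C, where severe COVID-19 is an effectiveness endpoint (Part B/C SAP, 3.3 and 5.3.2.2). The Part A SAP takes precedence over the protocol (Introduction), and its section 7 lists no changes from the protocol, so the narrowing is not declared.

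**Working it through.** **Date logic.** Let d = date of first reported severe sign minus date of positive RT-PCR, in days.

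| d | Window 0 to 28 | Strict window 1 to 28 | Window -14 to 28 |
|---|---|---|---|
| -3 | out | out | in |
| -1 | out | out | in |
| 0 | in | out | in |
| 1 | in | in | in |
| 28 | in | in | in |
| 29 | out | out | out |

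On either reading of the SAP sentence, d = -1 and d = -3 fail. Day 0 fails only on the strict reading. The SAP does not say which applies here, but its 28-day safety period after vaccination (Part A SAP, 6.1) counts the index day plus 27 more, which favours including day 0.

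**Does the later-of rule conflict with the window?** It compares the severe sign with the documented COVID-19 date, not with the test date. The documented date is itself the later of test and eligible symptoms (6.3.1.1). Suppose the positive test is on day 0, low oxygen saturation on day 1, and the second systemic symptom on day 3. COVID-19 is then documented on day 3, d = 1 is inside the window, and the severe event is dated max(3, 1) = day 3. The rule is therefore needed even with a one-sided window, and the section does not contradict itself. The mismatch is with Protocol 8.1.1 and with SAP 6.3.1.1 and 6.3.2.1.2.

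**Power.** Protocol Table 7 (9.3.1) gives 70.90% for 30 severe events, true VE 60%, null VE ≤ 0%. With 1:1 allocation and one-sided 0.025:

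power = Φ(|ln 0.4| × √d / 2 − 1.96), where d is now the number of events.

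For 30 events: 0.9163 × 5.477 / 2 − 1.96 = 0.549, and Φ(0.549) = 70.9%. The stated figure reproduces.

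No corrected figure can be computed, because the documents do not give the number of cases with a severe sign before the test. As scale only, if a test were run on the programmed set and a share of 30 severe cases were lost (assumed shares):

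| Assumed share lost | Events left | Power |
|---|---|---|
| 0% | 30 | 70.9% |
| 10% | 27 | 66.3% |
| 20% | 24 | 61.2% |
| 30% | 21 | 55.5% |
| 50% | 15 | 42.6% |

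None of these shares has a source in the documents.

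**The case against.** The strongest reply is that the efficacy analyses do not rest on the programmed set. SAP Part A, 6.3, states that adjudicated assessments were used in the two analyses already done and will be used in the final blinded analysis. The committee decides severe events and their dates (6.3.1.1), and the 11 severe cases reported for the first interim analysis are adjudicated (6.5). In Parts B and C adjudicated COVID-19 is again the primary approach, and the committee also adjudicates severe cases (Part B/C SAP, 5.3.1.1). No text binds the committee to the 28-day window. All of this stands.

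A reader might therefore infer too much: that anyone already severe when first tested drops out of the severe efficacy analysis, or that Table 7's power is overstated. Neither is supported. Severity first reported on the swab day is not clearly excluded. Nothing ties Table 7 or the 20-case trigger in SAP 6.5 to the programmed set.

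Frequency is also unproven. Participants receive the oxygen monitor at the Illness Visit (Protocol 8.1.3 and 8.1.4), where the swab is taken, so home readings would usually not come before it. That leaves mainly people assessed elsewhere first, such as those admitted to hospital.

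The 28 days could also be meant only as an upper limit on attribution, matching the 28-day Convalescent Period. That is plausible as intent, but a programmer following the sentence would still apply a lower limit at the test.

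**Conclusion.** The point holds for the programmed set. As written, a confirmed case whose first severe sign was reported on a date before the positive sample is not classed as severe. That is narrower than the protocol's definition and out of line with the two-sided rules for the other COVID-19 endpoints.

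The size is unknown. The documents give neither the number of such cases nor their split by arm, so no bias in VE is shown and no stated power figure is wrong. The adjudicated set is not shown to be affected, although no text says that the committee is exempt from the window. Same-day severity is an ambiguity.

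The conclusion assumes a literal reading of the window and use of the date on which the sign was first reported. The Part B/C SAP (Introduction) declares Part A analyses completed, so what can still be acted on is the derivation carried into Parts B and C and a re-check of the Part A programmed set.

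**What to change.** For the programmed set:

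- Replace the one-sided window with one open on both sides of the positive RT-PCR. An example is 14 days before to 28 days after, with day 0 included; the look-back mirrors the 14-day rule for COVID-19. If the one-sided window is intended, justify it and state how day 0 is treated.
- Take the severe-sign date as the earliest qualifying sign inside the window.
- Keep the later-of rule for the event date, so that a sign before the test is dated to the documented COVID-19 date.

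Apply this to the Part B/C derivation. State whether the Adjudication Committee uses the window. For Part A, do not redefine a completed analysis: rerun the programmed set with the wider window and report, as a sensitivity check, how many severe cases change and in which arm.

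The cost is a few SAP sentences, one edit to the derivation program, and one rerun. No new data are needed.
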